Specific Aims:

There are 3 specific aims for this study during the grant period:

- D. Develop a feasible protocol for obtaining QbMRI for children presenting to the emergency department with acute head injury.
- E. Prospectively test the diagnostic accuracy of qbMRI for detection of acute pediatric TBI in the emergency care setting compared to head CT as the reference standard.
- F. Evaluate the feasibility of obtaining QbMRI in the emergency department to assess acute pediatric brain injury, including need for sedative medications, time to imaging, and provider satisfaction.

Outcomes:

1. Primary Outcome: Test characteristics of QbMRI to detect acute pediatric TBIs, including sensitivity, specificity, positive/negative predictive value and positive/negative likelihood ratios.
2. Secondary Outcomes: Develop formal protocol to be employed for further clinical evaluation and trials on QbMRI in pediatric head trauma; assess feasibility of obtaining QbMRI in the emergency department to include need for anxiolysis/sedation, time to imaging and provider satisfaction.

Hypothesis:

We hypothesize there is no significant difference of sensitivity and specificity of QbMRI for detection of clinically important traumatic brain injuries as compared to non-contrast head CT in patients less than 15 years presenting with head trauma. We hypothesize that it will be feasible to obtain QbMRI in the emergency department without increased use of anxiolysis/sedation or prolonged time to obtain imaging

4. Study Design:

Overview: The study will be a prospective cohort study of diagnostic accuracy comparing QbMRI (index test) to non-contrast head CT (reference test). Children being evaluated for acute TBI with head CT will then undergo QbMRI in the emergency department. Only subjects who the attending physician has decided to obtain neuroimaging in will be enrolled; therefore subjects will not undergo imaging just for the study. The results of the QbMRI will not be used for clinical care. All images will be de-identified prior to review by the neuroradiologist including patient name, hospital and date.

5. Study Population:

Inclusion criteria:

1. The patient presents to the pediatric emergency department or trauma system at OHSU or is a trauma system transfer patient to OHSU
2. Age 0-14 years.
3. Being evaluated for a traumatic head injury and attending physician decides to obtain a head CT.

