QbMRIs will be obtained in the MRI scanner at OHSU available to the ED. The protocol will consist of a QbMRI protocol modified to include a blood-sensitive T2* sequence. No intravenous contrast will be administered. It is not anticipated that any sedation or anti-anxiety drugs will be administered to patients. However, this is reflected in the consent that a small portion of children will need for any type of neuroimaging. For this reason, parents may decline participation. No deep sedation drugs will be administered as that will fall under the definition of clinically unstable in the exclusion criteria. The protocol consists of:

- Coronal single-shot T2 weighted ultrafast spin echo
- Sagittal single-shot T2 weighted ultrafast spin echo
- Axial T2* weighted gradient recall echo

After a subject undergoes their imaging in the MRI suite, their further disposition will be selected by the attending physician as what they feel is necessary including admission to the hospital, observation or discharge.

Traumatic Brain Injury on neuroimaging will be defined as previously published¹ to include:

- Intracranial hemorrhage or contusion
- Cerebral edema
- Traumatic infarction
- Diffuse axonal injury
- Shearing injury
- Midline shift of intracranial contents or signs of brain herniation
- Skull fracture depressed by at least the width of the table of the skull
- Pneumocephalus

Number of Subjects:

A total of 100 subjects will be enrolled in this pilot study. To generate an approximate study timeframe and potential patient sample, EPIC was accessed to identify all patients less than 19 years of age who were seen in the OHSU emergency department in 2015 and had a “CT Head WO contrast (CPT code 70450)” performed while in the ED. This resulted 363 patients. As a large referral center, OHSU receives many transfers from outside hospitals. In our retrospective data of trauma system activations, the majority were transfer patients with head injuries. These numbers would not be included in the 363 most likely as their neuroimaging was done at an outside hospital. A review of the trauma registry at OHSU for the year of 2015 and patient less than 19 years of age resulted 221 patients who had head and neck injuries. There is most likely overlap between these 2 data points as some trauma registry patients were not transfers and underwent head CT in our department. However, we would conservatively expect that 400 patients may be eligible for this study during a 12 month period.

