
To assess the adequacy of this proposed pilot sample, we calculated the number of positive head CTs obtained in our department. Our rate of positive findings were better than the previous study mentioned rate of 2.5% positive head CTs of all ordered. At OHSU 10% of CTs in patients less than 19 years of age were positive for an acute intracranial injury. This was generated by applying the above search criteria in EPIC and associated an intracranial injury final diagnosis code including epidural hematoma, subdural hematoma, subarachnoid hemorrhage, intracranial bleed, skull fracture and cerebral contusion. This is a very conservative estimate as the majority of transfer patients through the trauma system will have positive neuroimaging as the reason for transfer and further pediatric subspecialty care. With these numbers we would expect to enroll the 100 patients within 1 year and have at least 10-20% with a positive acute TBI when taking into account the positive imaging rate in the OHSU emergency department and transfer patients with positive imaging.

Vulnerable Populations

This study, by design, is focused on pediatric patients. It may include other vulnerable populations such as pregnant women and minorities, though they are not the focus of the study

and are not included in screening criteria. No pregnant women will be given an MRI knowingly. Prisoners will not be included in this study.

Setting

The Doernbecher Children's Hospital emergency department

Consent Process

All parents will be consented on presentation to the emergency department by a member of the study team including the CRISP team. Please find attached consent form. All children ages 7-14 will be asked to signed the assent form as well.

We are requesting a consent/HIPAA waiver for a select group of patients. Any patient who is excluded from the study after initial screening for any reason other than the LAR refusing to be included will be reviewed by the principal investigator. If the clinical team, without any input from the research team, has obtained the same imaging test this study is evaluating, QuickBrain MRI, the study team will use the imaging and data as in the rest of the protocol under a waiver. It is not possible to obtain consent due to the short time window of being in the ED. Due to the acute nature of the injuries they do not have follow up in the ED either to allow consent.

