For patients who are excluded after the parent/LAR refuses the study, all charts will be reviewed. If the patient underwent the same imaging test this study is evaluating, QuickBrain MRI, by the clinical without any input from the research team, the patient family will be contacted by the study Principal Investigator as participation is generally declined in the trauma bay due to family stress. Unless at time of consent, study team noted reason for declining participation would be such that they would not be amenable to re-contact. The principal investigator will only discuss the study once with parents/LAR via phone number in EHR and detail that their child underwent the same imaging test we are studying. At that time, the principal investigator will ask for consent to include the patient in the study as nothing is needed in addition or further follow up. A telephone script has been uploaded to further detail this consent process.

Data Analysis:

All data will be entered into a RedCap database maintained on the OHSU network server requiring a username and password. Clinical data will consist of descriptive statistics. The primary outcome of whether a lesion was seen on QbMRI will be presented as sensitivity, specificity, negative predictive value and positive predictive value with 95% confidence intervals. The secondary outcome of whether patients need anxiolysis will be compared between head CT and QbMRI with an independent t-test. The QbMRI protocol will be described with language to describe the imaging.

Clearance of perivascular waist in the brain is critical for recovery after traumatic brain injury. Some of these clearance happens through a network of perivascular spaces surrounding the brain

vessels called the glymphatic system. When the glymphatic system becomes dysfunctional, enlarged perivascular spaces (ePVS) can be seen on MRI. The third outcome of this study is to evaluate the presence of ePVS in patients with concussion receiving an MRI during their emergency department evaluation. We hypothesize that changes in perivascular spaces happen over time, and therefore ePVS should not be present in these early studies.

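### One pooled PPV and NPV over in-house ED children and uncapped trauma transfers depends on the referral mix; below 100% specificity the PPV would read high for an in-house child whose CT result is not yet known

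*Combined protocol and SAP*

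**What the plan says.** All places are in the combined protocol and SAP.

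- **Who is enrolled.** Inclusion criterion 1 (5. Study Population) covers children presenting to the paediatric ED or trauma system and adds "or is a trauma system transfer patient to OHSU". Exclusion criteria 1 and 2 limit outside-hospital children only by the age of their CT (6 hours) and by whether the images are available. No cap or quota is set.
- **How often CT is positive.** Number of Subjects states: "At OHSU 10% of CTs in patients less than 19 years of age were positive for an acute intracranial injury". For transfers it says that "the majority of transfer patients through the trauma system will have positive neuroimaging as the reason for transfer". On the count of 363 in-department CTs, it says of transfers: "These numbers would not be included in the 363 most likely as their neuroimaging was done at an outside hospital". It also reports: "In our retrospective data of trauma system activations, the majority were transfer patients with head injuries". The two sources together are expected to yield "at least 10-20% with a positive acute TBI".
- **What is reported.** Outcomes lists as primary "sensitivity, specificity, positive/negative predictive value and positive/negative likelihood ratios". Data Analysis says: "The primary outcome of whether a lesion was seen on QbMRI will be presented as sensitivity, specificity, negative predictive value and positive predictive value". Each estimate is to carry a 95% interval. The section mentions neither origin nor a reference prevalence, and it leaves out the likelihood ratios.

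**The concern.** PPV and NPV depend on prevalence. On the protocol's own account, the two sources of subjects differ sharply in prevalence, because most transfers arrive after a scan has already been read as positive. The transfer share therefore helps to set the primary PPV, and that share is neither planned nor stated.

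Objective B asks about accuracy in emergency care. A predictive value is most useful there for a child who has not yet had a CT result. A pooled PPV read as the answer for that child would be partly a product of referral, and it would not carry over to the larger multicentre study that this pilot is meant to inform, where the mix would differ. More subjects with the same mix would not remove the difference.

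**Working it through.** **Inputs.** From Number of Subjects: 363 in-department CTs, 10% positive, 400 eligible per year, 221 trauma-registry patients with unknown overlap. From Preliminary Data: sensitivity 85% for any radiographic injury. Not in the documents, so assumed: specificity; transfer positivity of 50% to 100% (the text says only a majority); and that the 400 − 363 = 37 further children are all transfers.

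**Step 1: the plan's expected prevalence.** Pooled prevalence = (363 × 0.10 + 37 × pT) / 400.
- pT = 0.50: (36.3 + 18.5) / 400 = 13.7%.
- pT = 1.00: (36.3 + 37) / 400 = 18.3%.

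Both lie inside the 10% to 20% that the plan expects.

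**Step 2: predictive values with equal accuracy by origin.**
PPV = p·Se / [p·Se + (1−p)(1−Sp)]; NPV = (1−p)·Sp / [(1−p)·Sp + p(1−Se)]; Se = 0.85.

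| Assumed Sp | In-house PPV (10%) | Pooled PPV (13.7% to 18.3%) | Gap, points |
|---|---|---|---|
| 90% | 48.6% | 57.4% to 65.6% | 8.8 to 17.0 |
| 95% | 65.4% | 73.0% to 79.2% | 7.6 to 13.8 |
| 99% | 90.4% | 93.1% to 95.0% | 2.7 to 4.6 |
| 100% | 100% | 100% | 0 |

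Example at Sp 95%: in-house 0.085 / (0.085 + 0.045) = 65.4%; pooled at 13.7%, 0.11645 / (0.11645 + 0.04315) = 73.0%.

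NPV at Sp 95% is 98.3% in-house and 97.6% to 96.6% pooled.

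**Step 3: what moves the gap (Sp 95%).**
- *Higher in-house rate.* The 10% counts all head CTs with no trauma filter. If 60% were for trauma (assumed), the rate is 0.10 / 0.60 = 16.7% and in-house PPV is 77.3%. With the transfer share held at 37/400, pooled prevalence is 0.9075 × 0.1667 + 0.0925 × pT = 19.8% to 24.4%. Pooled PPV is then 80.7% to 84.6%, a gap of 3.4 to 7.3 points.
- *Larger transfer share.* If all 221 registry patients were additional transfers (an upper bound), prevalence is (36.3 + 221 × pT) / 584 = 25.1% to 44.1%, and pooled PPV is about 85% to 93%.

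**Step 4: is the direction secure if accuracy differs by origin?**
- *PPV.* Post-test odds = prevalence odds × LR+. With only 51% of transfers positive, the ratio of prevalence odds is (0.51/0.49) / (0.10/0.90) = 9.4. The direction reverses only if LR+ in transfers is below about one ninth of the in-house LR+. Against 16.7% in-house, the ratio is 5.2 and the threshold about one fifth.
- *NPV.* At sensitivity 100%, NPV is 100% at any mix. Suppose instead a transfer share of 20%, 75% of transfers positive, sensitivity 100% in transfers and 85% in-house, and Sp 95% (all assumed). Pooled prevalence is 0.20 × 0.75 + 0.80 × 0.10 = 23%. Pooled NPV is 0.7315 / (0.7315 + 0.012) = 98.4% against 98.3% in-house, so the sign flips.

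**Step 5: sampling error.** At Sp 95% and n = 100, the pooled PPV rests on about 16 to 20 MRI-positive children: 100 × (0.11645 + 0.04315) = 16.0 at 13.7% prevalence, and 19.6 at 18.3%. In an assumed sample of 80 in-house children (8 positive) and 20 transfers (12 positive), pooled PPV might be 17/21 = 81%, exact 95% CI 58% to 95%. That interval includes 65.4%.

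**The case against.** The strongest reply is that the pooled PPV is not wrong. Transfers are named in the inclusion criteria and counted in the expected yield, and the hypothesis concerns children under 15 presenting with head trauma. Nothing formally limits the target to children with an unknown CT result. This stands: the pooled values are correct for the enrolled sample, and they mislead only when applied to the in-house child. Objective B's reference to emergency care makes that application natural, so the distinction should be stated.

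Second, no specificity is given, and at 100% there is no gap. This also stands, and the conclusion is conditional for that reason.

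Third, sensitivity and specificity are reported, so a reader could rescale to any prevalence. This holds only if accuracy is similar by origin, which the planned report would not let a reader check.

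Fourth, pooling is inferred from silence, and a split remains possible at write-up. True, but Data Analysis as written asks for one set of values, and nothing in it prompts the split.

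Finally, the shift is within sampling error in a 100-subject pilot. That limits the weight of the point. It does not remove it, because a confidence interval covers chance and not a difference in target population.

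**Conclusion.** The point holds in a conditional form. If specificity is below 100% and accuracy is broadly similar by origin, the pooled PPV will exceed the PPV for an in-house child whose CT result is unknown. On the 363 + 37 reading, the excess is about 8 to 14 points at specificity 95% and about 3 to 5 points at 99%. These figures rest on the assumed specificity, on transfer positivity of 50% to 100%, on sensitivity of 85%, and on the 10% in-house rate. That rate is itself approximate: it covers ages under 19 rather than 0 to 14, has no trauma filter, and counts any skull-fracture code, whereas the study definition requires a depressed fracture.

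Three stronger readings are tempting but not supported:
- *That PPV would move from 65.4% to 81.0% at specificity 95%.* This sets 10% against 20% prevalence, but those are the two ends of one whole-sample range and not an in-house value and a pooled value.
- *That the pooled NPV is too low.* That needs similar sensitivity by origin, below 100%; otherwise the error can vanish or reverse.
- *That the sample size or the pooled sensitivity and specificity analysis must change.* Prevalence does not enter sensitivity and specificity directly, and nothing here alters the 100 subjects.

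This is a worthwhile, low-cost reporting improvement. It is not a threat to the study.

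**What to change.** Amend Data Analysis as follows.

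1. Record origin (in-house or transfer). Report the number, observed prevalence and 2x2 table for each, descriptively and without tests.
2. Give in-house PPV and NPV with exact 95% CIs as the estimate for the ED child. Label the pooled PPV and NPV as specific to this sample's mix. Keep overall sensitivity and specificity as planned.
3. If predictive values at a named prevalence are also shown, use in-house sensitivity and specificity, or state the assumption of equal accuracy by origin. With sensitivity 95% in transfers and 85% in-house, and the other Step 4 assumptions for NPV, pooled sensitivity is (0.1425 + 0.068) / 0.23 = 91.5%. Bayes' rule at 10% prevalence then gives NPV 99.0% when the in-house value is 98.3%.
4. As a separate correction, add LR+ and LR− with 95% CIs, since Outcomes lists them as primary.

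**Cost.** Wording only: outside-hospital origin is already checked at screening through exclusion criteria 1 and 2. The downside is wide in-house intervals. In the 80/20 illustration, in-house PPV is 7/11 = 64%, exact 95% CI 31% to 89%, and in-house NPV is 68/69 = 98.6%, CI 92.2% to 99.96%. That example rounds to whole children and places all four false positives in-house, so its PPV gap is not due to prevalence alone.

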Rapid MRI for Acute Pediatric Head Trauma

NCT03291964

7/19/2017

1. Protocol Title: QuickBrain MRI for Pediatric Head Trauma: A Pilot Study

2. Objectives:

- A. Develop a feasible protocol for obtaining QbMRI for children presenting to the emergency department with acute head injury.
- B. Prospectively test the diagnostic accuracy of qbMRI for detection of acute pediatric TBI in the emergency care setting compared to head CT as the reference standard.
- C. Evaluate the feasibility of obtaining QbMRI in the emergency department to assess acute pediatric brain injury, including need for sedative medications, time to imaging, and provider satisfaction.

3. Background:

Pediatric head trauma remains a frequent reason for children to visit the emergency department (ED).¹ The current standard of care is to identify clinically important traumatic brain injury (ciTBI) which is defined as injuries that require surgical intervention, hospital length of stay greater than 2 days, intubation or result in death. This standard is used rather than “radiographic injuries” as this identifies lesions that require clinical intervention and observation rather than things that may be imaging artifact or so small that they are not clinically relevant. A majority of children with head injuries present to the ED with mild symptoms and Glasgow Coma Scale (GCS) scores of 14 or 15 resulting in a relatively low risk of a ciTBI that require neuroimaging.² However, due to the potential consequences of missed intracranial injury, CT imaging is frequently employed to further evaluate these patients. This concern is part of the cause for the dramatic increase in the rate of CT imaging over the last 10-20 years.³ A recent Pediatric Emergency Care Applied Research Network (PECARN) study addressed this issue and developed a highly sensitive clinical decision rule that identified children at low risk of ciTBI that may not need head imaging.¹ In many clinical scenarios, this rule has the potential to substantially reduce CT use. However even when this rule is applied, the majority of CT scans obtained are negative, exposing children unnecessarily to ionizing radiation.

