Our initial retrospective study suggests that QbMRI has adequate sensitivity to detect acute ciTBIs in children. The study was presented at 2 national conferences in the spring of 2016 (Society for Academic Emergency Medicine and Pediatric Academic Society) with a manuscript currently under review.¹² This preliminary study included all pediatric trauma patients presenting to OHSU from 2/2010 through 12/2013 who had both a head CT and QbMRI. The current standard of care in the pediatric ICU at OHSU is for patients admitted with an acute head injury to undergo routine QbMRI follow up to assess status of the injury rather than a repeat head CT. Our study team collected clinical data on these patients that included clinical interventions and then de-identified all head CT and QbMRI images for this cohort. The images were then independently reviewed by 2 neuroradiology fellows at OHSU (Please refer to **Figure 1**). The sensitivity of QbMRI to detect any radiographic injury was 85% (95% CI: 73, 93), but increased when evaluating clinically important TBIs to 100% (95% CI: 89, 100). The largest limitation of this study was the variable and often long time interval between acquisition of the head CT and QbMRI. The average length of time between the initial head CT and QbMRI was 27.5 hours with only 41% receiving both imaging tests within 12 hours of each other. Also, our preliminary data was collected by retrospective review. As such, it is very promising that our initial study had high sensitivity, but further prospective pilot data with a shorter interval between the index and reference test is needed to assess the discrepancy between the two types of lesions (radiographic vs clinically important) and feasibility of obtaining qbMRI in the setting of acute pediatric head trauma. While our study did not miss any clinically important TBIs, on further review of radiographic “missed lesions”, the study pediatric neurosurgeon noted signs of a healing bleed. This may suggest that they were “missed” because they were healed rather than present and not seen. All patients that did not have a lesion identified on QbMRI did not require significant clinical interventions and only underwent periods of observation in the hospital. However, this raises the need for a prospective trial to obtain QbMRI imaging within the same time frame sequentially after the initial head CT. The current proposed pilot study will provide further data to guide a larger, future multicenter study.

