4. Clinically stable for additional testing: provider deems it safe to obtain a QbMRI in the ED without deep sedation

Exclusion criteria:

1. Subject is from outside hospital and head CT was performed greater than 6 hours prior
2. Subject is from outside hospital and initial head CT is not in our imaging system for review
3. History of intracranial surgery
4. History of metallic implants making MRI contraindicated
5. Decompressive surgery prior to QbMRI

Study Procedure:

The Clinical Research Investigative Study Program (CRISP) volunteers who are on duty in the emergency department between the hours of 7 am and 11 pm will screen all ED patients for eligibility including pediatric trauma system entries. They will identify possible subjects based on suggestive chief complaints (e.g. head injury, trauma, fall, etc.) and approach the attending physician about whether the subject is being evaluated for possible acute head injury and will be receiving neuroimaging. If so, they will approach the family and review the consent forms with them for participation. After subjects are found to be eligible (see above inclusion/exclusion criteria) and consented, the physician will order the study QbMRI to be done after the head CT. QbMRIs are available to our pediatric ED at all hours as it is standard of care for other indications as described previously. Subjects will only be enrolled in the study if the attending physician feels they warrant neuroimaging with a head CT. After undergoing a QbMRI, their clinical care will be the same whether they are in the study or not. A copy of the images will then be de-identified and placed in separate review folders in the electronic radiology system so they cannot be linked (ie. One folder for head CTs and one folder for QbMRIs) for review by an attending neuroradiologist. Clinical data including length of stay, procedures performed and disposition will be collected directly from EPIC.

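### The waiver and re-contact rules can bring clinical QbMRIs from outside the study's ED process into feasibility outcomes that are defined for the ED

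*Combined protocol and SAP*

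**What the plan says.** Item C of Objectives sets the feasibility aim: "Evaluate the feasibility of obtaining QbMRI in the emergency department to assess acute pediatric brain injury, including need for sedative medications, time to imaging", with provider satisfaction as the third component. The secondary outcome under Outcomes names the same setting: "assess feasibility of obtaining QbMRI in the emergency department to include need for anxiolysis/sedation, time to imaging and provider satisfaction". The Hypothesis paragraph expects that "it will be feasible to obtain QbMRI in the emergency department without increased use of anxiolysis/sedation or prolonged time to obtain imaging".

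Study scans are restricted to match. Inclusion criterion 4 in Study Population requires that the "provider deems it safe to obtain a QbMRI in the ED without deep sedation". Study Procedure adds: "No deep sedation drugs will be administered as that will fall under the definition of clinically unstable in the exclusion criteria".

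Consent Process then opens two further routes into the study.

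- **Waiver.** A child excluded after screening for a reason other than refusal is reviewed. If the clinical team had independently obtained a QbMRI, "the study team will use the imaging and data as in the rest of the protocol under a waiver".
- **Re-contact.** A child whose family refused, and who had a clinical QbMRI, can be added if the family agrees in a single telephone call.

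Both routes put the same condition on the scan: it must be the test under study, and the research team must have had no part in ordering it. Data Analysis says "The secondary outcome of whether patients need anxiolysis will be compared between head CT and QbMRI", by an independent t-test. It names no specific analysis of time to imaging and makes no split by route of entry.

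**The concern.** The feasibility question is about one process: a child in the ED has a head CT, and a QbMRI follows there without deep sedation. The two extra routes select children differently. They enter because a QbMRI was done for clinical reasons and, in the waiver group, after having been excluded from the study. If their sedation and timing are pooled with those of consented children, the result describes a mixture whose make-up depends on how many were added and why.

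Feasibility is one of three aims and has its own hypothesis, and Preliminary Data says the pilot is meant to guide a larger multicenter study. A sedation or timing figure that does not describe the ED process would be a poor basis for planning that study. The point concerns sedation and time to imaging, not the accuracy results.

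**Working it through.** The plan states no expected feasibility figure and no number of waiver or re-contact children, so there is nothing to reproduce. The main check is of the text. The arithmetic that follows only shows scale.

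**1. Who can re-enter.** Setting the criteria in Study Population beside the waiver:

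- A child who fails inclusion criterion 4 because deep sedation is needed has been excluded for a reason other than refusal. With a clinical QbMRI, the child qualifies for the waiver, although Study Procedure rules out deep sedation for study scans.
- A child excluded under exclusion 5 (decompressive surgery before QbMRI) qualifies in the same way, with a scan that is post-operative by definition.
- A child excluded under exclusion 1 (outside CT more than 6 hours old) qualifies too.
- Inpatient scans are possible. Preliminary Data describes pediatric ICU practice at the site in these words: "patients admitted with an acute head injury to undergo routine QbMRI follow up to assess status of the injury rather than a repeat head CT". Nothing in the waiver or re-contact text excludes such a scan.

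**2. QbMRI sedation rate.** Inputs: 4% for consented children (Background, from an earlier shunt study). Assumed: w added children out of 100, of whom a share s was sedated. Pooled rate = [(100 − w) × 0.04 + w × s] / 100. For example, w = 10 and s = 0.25 gives (3.6 + 2.5)/100 = 6.1%.

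| w | s = 10% | s = 25% | s = 50% |
|---|---|---|---|
| 5 | 4.3% | 5.05% | 6.3% |
| 10 | 4.6% | 6.1% | 8.6% |
| 20 | 5.2% | 8.2% | 13.2% |

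For comparison, the exact 95% confidence interval for 4 of 100 is 1.1% to 9.9%. Only the last cell lies outside it.

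**3. The planned comparison.** Data Analysis compares QbMRI with CT, so the CT side matters. If consented children have the same rate for both scans, the pooled difference is (w/100) × (s for QbMRI − s for CT). With w = 10 and 50% sedated for QbMRI, it is 0 points if the same share was sedated for CT, and 0.10 × 0.50 = 5 points if none was. It is negative if more were sedated for CT than for QbMRI. The documents give no CT sedation figure for these children.

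**4. Time.** Inputs: 27.5 hours mean CT-to-QbMRI interval in the retrospective cohort (Preliminary Data). Assumed: a 2-hour mean in the ED. Pooled mean = [(100 − w) × 2 + w × 27.5] / 100, which is 3.3, 4.6 and 7.1 hours for w = 5, 10 and 20. With ED means of 1 and 4 hours and w = 10, it is 3.7 and 6.4 hours. This treats every added scan as a late one. If 10 children are added and only 5 are late, the others matching the ED mean, the result is that for w = 5, or 3.3 hours. The protocol never defines time to imaging as the CT-to-QbMRI interval, so even the scale is an assumption.

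**The case against.** The strongest reply is that the outcome carries its own limit. Feasibility is worded as obtaining QbMRI in the ED, so an ICU scan is not an instance of it, and using the data in line with the rest of the protocol could be read as pointing back to that wording. The waiver is also justified by the brief ED stay, and the stated Setting is the ED. This makes a reading limited to ED-visit scans plausible, and it is why inpatient scans are called only possible here.

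The reply does not dispose of the point. The brief ED stay explains why consent is missing and does not restrict the scan. The deep-sedation limit sits in eligibility and procedures, not in the outcome wording, and eligibility cannot be restored for children who are in the waiver group because they were excluded. A child excluded under criterion 4 would enter even on the ED-visit reading.

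Four stronger conclusions that a reader might draw are not supported:

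- **That the sedation rate would double or triple.** More than doubling at 10 added children, or tripling at 20, needs the assumed 50% sedation rate. At 10% the pooled rates are 4.6% and 5.2%.
- **That these children would decide the feasibility hypothesis.** The hypothesis is about increased use of sedation, and their CT sedation is unknown.
- **That success in obtaining the scan is inflated.** Every added child does have a scan, but scan completion is not a listed outcome.
- **That the groups could never be separated.** This is true of a published pooled figure. With route of entry recorded, the data can be split.

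It is also fair to say that dropping all these children would be too broad. Some refusers may have been scanned in the ED without deep sedation. Study Procedure notes that parents may decline because some children need sedation, so removing refusers entirely could itself distort the sedation rate. The fix takes this into account.

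**Conclusion.** The concern holds as a conflict between sections. The outcome and eligibility wording describes QbMRI in the ED without deep sedation, while the waiver and re-contact rules admit clinical QbMRIs with no stated limit on place, time or sedation, and the analysis does not separate them. Followed literally, the plan lets children from outside the ED process into the sedation and time results.

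The size and direction are unknown. The number of added children, their sedation for either scan and the ED mean time are all assumptions in the figures above. The 4% comes from a shunt study and the 27.5 hours from a retrospective cohort. Time could also move either way: late scans lengthen it, but a clinically ordered scan needs no research consent and might be quicker. The documents do not show that the feasibility conclusion would change. The change is still worth making, because the conflict is in the stated rules and the remedy costs little.

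**What to change.** 1. In REDCap, record for every QbMRI the route of entry (consented in the ED, waiver, re-contact), the place and time of the scan, and any sedation.
2. In Data Analysis, add wording such as:

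> The main analysis of anxiolysis/sedation and time to imaging, and of the hypothesis on both, will use children consented in the ED whose study QbMRI was ordered there. Children included by waiver or re-contact will be reported separately by route. A sensitivity analysis will add those whose clinical QbMRI was done during the ED visit and within the limits set in Study Population and Study Procedure.

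3. In Consent Process, amend the sentence on using waiver data so that it refers to this rule for the feasibility outcomes, and say the same for re-contacted children.
4. Reconcile Study Population and Study Procedure with Consent Process on place, time and sedation. Which clinical limits should apply is for the investigators to settle.

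Under the sensitivity analysis, a re-contacted refuser scanned in the ED could count, as could a waiver child missed for a practical reason. A waiver child excluded for failing a criterion would not.

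The cost is a few sentences, a few database fields and a slightly smaller denominator for the main feasibility analysis. No extra patients, scans or readers are needed.
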